8.1 Screening/Baseline Assessments and Procedures

1. Informed Consent Process:
 - We will obtain informed consent from participants, ensuring they understand the nature of the trial, potential risks and benefits, and their rights as participants.
2. Medical History and Physical Examination:
 - We will collect relevant medical history information, including past medical conditions, current medications, surgical history from the survivor.
3. Work-related Assessments:
 - We will conduct baseline assessment on pre-cancer work data - work hours, number of sick days taken; current status - if and since when they are on short term or long term disability from the survivor
4. Disease Assessment and Staging:
 - We will collect survivor reported disease assessments specific to the cancer types under study, such as tumor staging, biomarker evaluations, or imaging studies to assess baseline disease status and severity.
5. Stratification Variables:
 - See section 5.3 for Trial population variables and section 4.1 for Randomization variables.

8.2 Efficacy Assessments and Procedures

Improvement in Quality of Life (QoLS) as measured by FACT-G questionnaire (Trial Objective 1):

- Endpoint: Change in FACT-G scores measuring quality of life
- Assessment Procedures: Administer the above four questionnaires to assess participants' at baseline and specified time points during and after the intervention period.
- Data Collection: Obtain self-reported scores from participants on Quality of Life.

- Analysis: Calculate the mean difference in change in scores between the intervention and control groups at each time point to evaluate the impact of the intervention.

Reduction in Employee Absenteeism (Trial Objective 2):

- Endpoint: Number of leave days taken by employed cancer survivors due to health issues.
- Assessment Procedures: Track the number of leave days (sick leave, short-term disability, long-term disability) taken by participants in both groups throughout the trial period.
- Data Collection: Obtain leave records from participants' employers or self-reported information from participants.
- Analysis: Compare the average number of leave days between the intervention and control groups to assess the impact of the intervention on reducing absenteeism.

Improvement in Employee Presenteeism (Trial Objective 3):

- Endpoints: Motivation to work (self-reported scales/questionnaires), performance review scores (from employer records or self-reported evaluations).
- Assessment Procedures: Administer self-reported scales/questionnaires to assess participants' motivation to work and obtain performance review scores from employer records or self-reported evaluations.
- Data Collection: Collect self-reported data on motivation to work and obtain performance review scores from participants and their employers.
- Analysis: Compare the mean scores of motivation and performance reviews between the intervention and control groups to evaluate the impact of the intervention on enhancing presenteeism.

8.3 Safety Assessments and Procedures

- Responsibilities

- The Trial Monitoring Committee will oversee safety assessments and procedures throughout the trial.
- Safety Data Collection
 - Safety data will be collected through self-reported participant interviews.
 - Standardized forms and procedures will be used for consistent data collection across study sites.
- Safety Reporting and Management
 - Procedures will be in place for the timely reporting and management of safety events, including serious adverse events (SAEs) and suspected unexpected serious adverse reactions (SUSARs).
- Safety Monitoring Committee
 - The Trial Monitoring Committee will review safety data periodically, assess participant safety, and provide recommendations to the study team.
- Participant Education and Counseling
 - Participants will receive education and counseling regarding potential safety risks associated with the intervention.
 - Open communication between participants and study staff will be encouraged to facilitate early detection and reporting of safety events.
- Risk Mitigation Strategies
 - Risk mitigation strategies will be implemented to minimize potential safety risks associated with the intervention, such as user training and device monitoring.
 - Adherence to safety protocols will be monitored, and interventions will be implemented to address deviations or non-compliance.
- Regulatory Compliance
 - Compliance with regulatory requirements governing safety reporting will be ensured, including adherence to Good Clinical Practice (GCP) guidelines and ICH regulations.

- Accurate and comprehensive safety documentation will be maintained, including safety reports and investigator brochures.

8.4 Adverse Events and Serious Adverse Events

A serious adverse event (SAE) in this trial is defined according to the following severity grades:

- Grade 1: Mild discomfort, not interrupting normal activities
- Grade 2: Moderate discomfort, interrupts normal activities but not incapacitating
- Grade 3: Severe, resulting in disability or necessitating medical consultation (SAE)
- Grade 4: Requires hospitalization (SAE)
- Grade 5: Results in death (SAE)

Only events classified as Grade 3, 4, or 5 are considered SAEs within the context of this trial

- Time Period and Frequency for Collecting SAE Information
 - Time period
 - Start: Apr 15, 2024
 - End: Oct 15, 2025
 - Frequency
 - SAEs will be documented as they are reported by participants.
- Recording of SAEs
 - While prior studies suggest minimal evidence of SAEs resulting from exercise, diet, or meditation in cancer survivors, all SAEs encountered during this trial will be meticulously recorded. Participants can report SAEs directly via the app, or coaches may report on their behalf. Reports should include the severity grade, description of the event, and the participant's perspective on whether the SAE was related to trial interventions.
- Follow up of SAEs

- All participants will continue receiving standard care from their healthcare providers. In the event of an SAE, a dedicated physician will be assigned to assess the situation, provide immediate recommendations, and categorize the cause of the SAE based on discussions with the participant. This classification will also be documented.
- Regulatory Reporting Requirements for SAEs
 - SAEs must be reported to the Institutional Review Board (IRB) within 24 hours of the event's identification. Additionally, the Sponsor will ensure prompt notification of all investigators regarding any SAEs, enabling them to inform participants about potential risks and take any necessary precautions.
- The grading of adverse events is aligned with the Common Toxicity Criteria for Adverse Events (CTCAE) standards, which detail adverse events on a scale from 1 to 5. The complete CTCAE documentation is available on the National Cancer Institute's website: [NCI CTCAE Information](#).

Section 9: STATISTICAL CONSIDERATIONS

The analysis will be conducted on all participant data at the end of 3 months, 6 months, 12 months and 18 months (ie. end of the trial).

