6.4 Treatment of Overdose

While overdose typically refers to the administration of excessive doses of pharmacological agents, in the case of a software solution, it pertains to the potential for participants to overexert themselves during exercise sessions, leading to adverse effects

such as muscle strains, joint injuries, fatigue, or exacerbation of underlying health conditions.

Given the nature of the trial intervention, there are no specific antidotes or therapies for trial intervention overdose. However, measures will be in place to prevent and manage potential adverse events associated with excessive exercise. These measures include:

- Individualized Exercise Prescription: The software app provides personalized exercise coaching tailored to each participant's fitness level, health status, and exercise tolerance through an intake form. Each patient is categorized into low or moderate based on the form. Exercise sessions will be designed to gradually progress in intensity and duration for each individual based on participants' responses and feedback.
- Monitoring and Supervision: Participants will be closely monitored during exercise sessions by trained exercise coaches who can provide real-time feedback and guidance. Coaches will ensure that participants adhere to safe exercise practices and modify activities as needed to prevent overexertion or injury. The survivor will be filling a RPE (Rating of Perceived Exertion) form after each session and will be given feedback based on the same.
- Participant Education: Participants will receive education and instruction on proper exercise techniques, warm-up and cool-down procedures, and signs of overexertion or injury. They will be encouraged to listen to their bodies and communicate any discomfort or concerns to their exercise coach.
- Flexibility and Adaptability: The solution app offers flexibility in scheduling and adapting exercise sessions to accommodate participants' individual preferences, capabilities, and constraints. Participants have the autonomy to adjust the intensity or duration of exercises based on their comfort level and feedback from the exercise coach.
- Prompt Recognition and Response: In the event of symptoms suggestive of overexertion or adverse effects during exercise sessions, participants will be

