9.4 Safety Analyses

- We shall continuously monitor and document all serious adverse events (SAEs), categorizing them by severity, causality, and timing relative to the intervention. This includes both anticipated events related to cancer and potential unexpected events related to the intervention.

- Comparative Analysis: Compare the incidence rates of SAEs between the intervention and control groups. This can help ascertain whether the intervention group experiences a higher rate of events, indicating potential safety concerns.
- The Trial Monitoring Committee shall regularly monitor these and can decide to forfeit the trials when there are clear indications that safety of the survivor is in danger due to our intervention
- Along with that we shall utilize QoL and well-being measures to indirectly assess safety, as significant declines could indicate adverse impacts of the intervention.

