9.7 Sample Size Determination

- The metric-wise sample size calculation is provided in the table below on alpha as 0.05 and power of 80% for the one-tail test at enrollment ratio = 1.
- While we are conducting the power analysis and sample size calculation based on several variables (outcomes) of interest, the sample size was computed separately for each parameter in the study and the greatest is used to obtain sample size.
- The analysis (detailed below in table) showed that sample of size of 102 is powerful enough for the analysis to cover 100% of primary and secondary metrics.
- Now since we believe that the long follow-up duration of 6 months for our trial will lead to around 30% drop-offs, we decided a final sample size of 146 (73 control, 73 test).

- So even if get 30% or 44 participants drop off we end up with final sample set of 102 (51 control, 51 test) and would be able to come to statistically significant effects ($p < 0.05$) with respect to 100% of primary and secondary metrics.

Metric Segment	Sub Metric	Control Data	Test Data	Assumed Variance	Sample Size
Primary Outcome / Concerns					
Quality of Life Improvement	QoLS Score (FACT-G)	70	85	Variance of 20	42 (21 Control, 21 Test)
Secondary Outcome / Concerns					
Presenteeism	Attitude towards work	2	4	Variance of 1.5	16 (8 Control, 8 Test)
	Employee Performance	0.6	0.7	Variance of 20%	102 (51 Control, 51 Test)
Absenteeism	Working Hours	30	40	Variance of 10	28 (14 Control, 14 Test)
	Vacation Days	0.5	0.3	Variance of 0.15	16 (8 Control, 8 Test)
Exploratory Outcomes					
Cancer Care	Cancer Progression Status	0.85	0.88	Variance of 0.04	46 (23 Control, 23 Test)

	Cancer recurrence status	0.3	0.21	Variance of 10%	32 (16 Control, 16 Test)
Medical Expenditure	Total Healthcare Expenditure (Planned + Unplanned)	10000	8000	Variance of 4000	102 (51 Control, 51 Test)
	No of Urgent Care Visits	3	2.5	Variance of 0.5	28 (14 Control, 14 Test)
	No of ED Visits	5	3.45	Variance of 0.8	10 (5 Control, 5 Test)
	No of unplanned outpatient/office visits (other than ED)	4.28	3.5	Variance of 0.8	28 (14 Control, 14 Test)
	Unplanned Hospitalisations	5	4	Variance of 0.8	18 (9 Control, 9 Test)
	Length of hospital stay	3	2	Variance of 0.8	18 (9 Control, 9 Test)
	No of planned outpatient visits	2	1.8	Variance of 0.3	58 (29 Control, 29 Test)
	No of planned hospital visits	1.25	1	Variance of 0.1	10 (5 Control, 5 Test)
	Length of hospital stay	3	2	Variance of 0.8	18 (9 Control, 9 Test)

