10.2 Committees

The trial will establish an Trial Monitoring Committee (TMC) to oversee the safety and integrity of the trial. The TMC will consist of independent experts in relevant fields such as oncology, biostatistics, and cancer exercise specialists. Their primary role will be to review safety data at regular intervals during the trial to ensure participant safety.

Trial Monitoring Committee will perform safety assessments every 6 months. But they will meet more often if needed such as in case of increase in AEs. The Trial Monitoring Committee will be responsible for making a determination of continuing the study based upon results of the safety assessment.

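### The between-arm SAE comparison in section 9.4 is weak and open to ascertainment bias: minor exercise harms have no defined capture, only the coached arm has a second reporting route, and the SAE definition can take in ordinary cancer care.

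*Protocol*

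**What the plan says.** The Combined protocol and SAP carries the same wording as the Protocol in 8.4 and 9.4, so the point applies to both.

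- **Definition (8.4).** "Only events classified as Grade 3, 4, or 5 are considered SAEs within the context of this trial". The Grade 3 entry is "Grade 3: Severe, resulting in disability or necessitating medical consultation (SAE". Grade 4 is any event requiring hospitalization; planned admissions are not mentioned. The section also says that its grading is aligned with CTCAE.
- **Collection (8.4).** "SAEs will be documented as they are reported by participants", and "Participants can report SAEs directly via the app, or coaches may report on their behalf". The rules on period, recording and follow-up are written for SAEs only.
- **Analysis (9.4).** "Compare the incidence rates of SAEs between the intervention and control groups". A higher rate in the intervention group is to be read as a possible safety concern.
- **Expected harms (2.2 and 6.4).** Overexertion may cause effects "such as muscle strains, joint injuries, fatigue, or exacerbation of underlying health conditions".
- **Oversight (9.6 and 10.2).** An unacceptable rate of adverse events, with no number attached, is a criterion for early stopping or adaptation. The Trial Monitoring Committee reviews safety every six months: "But they will meet more often if needed such as in case of increase in AEs".
- **Other capture.** Section 8.3 mentions participant interviews on standardized forms, without a frequency or a grade range. The schedules in 6.1 have no adverse-event row in either arm.

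**The concern.** Three features of the plan act on the same comparison.

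First, the harms that the plan itself expects will often be Grade 1 or 2. These have no scheduled capture and no analysis, although the oversight sections assume that an adverse event rate will exist.

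Second, test participants meet a coach at 3 to 5 live sessions a week, and the coach may report for them. Control participants have no coach. The same event is more likely to be recorded in the test arm, which pushes the comparison towards a false signal of harm.

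Third, participants have Stage 1 to 4 cancer and continue standard care. A definition that can take in consultations and all admissions raises the background SAE rate in both arms and makes a programme-related excess harder to see.

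The second feature can create a signal and the third can hide one. A higher or lower SAE rate in the test arm would then be hard to interpret, although it is the only formal between-arm safety comparison and informs the committee's advice on continuing.

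**Working it through.** **1. The plan's own figures.** Section 9.7 reaches 102 evaluable participants and 146 randomized. The Employee Performance row (0.6 against 0.7), with its stated variance of 20% read as an SD of 0.20, one-sided alpha 0.05 and 80% power, gives 50.15 per arm by t-test. That rounds up to 51 per arm, or 102. Then 102 / (1 − 0.30) = 145.7, rounded up to 146. Both figures reproduce. They rest on efficacy metrics; no SAE rate, safety power or numerical safety threshold is given.

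**2. Method for the illustrations.** Everything from here rests on assumed rates. I take the proportion of participants with at least one SAE, 73 per arm, and a two-sided 5% test:

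power = Φ[(d − 1.96 × se0) / se1], where d is the difference in proportions, se0 = √(2p̄(1 − p̄)/73), p̄ is the mean of the two proportions, and se1 = √((p1(1 − p1) + p2(1 − p2))/73).

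**3. Unequal reporting, no true harm.** If the true rate is r in both arms, and shares s_c (control) and s_t (test) are reported, the observed risk ratio is s_t / s_c whatever r is. With 60% and 90%: 0.90 / 0.60 = 1.5.

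Example with r = 20%: the observed rates are 0.12 and 0.18, se0 = 0.0591 and se1 = 0.0589. Then (0.06 − 1.96 × 0.0591) / 0.0589 = −0.95, and Φ(−0.95) = 0.17.

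Chance of a significant excess in the test arm (nominal 2.5%):

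| Reported, control / test | Risk ratio | r = 10% | 20% | 30% | 50% |
|---|---|---|---|---|---|
| 60% / 75% | 1.25 | 5.5% | 7.6% | 9.9% | 15.7% |
| 60% / 90% | 1.50 | 10.1% | 17.2% | 25.4% | 46.4% |
| 80% / 95% | 1.19 | 5.1% | 6.9% | 9.0% | 14.7% |

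**4. Dilution.** Suppose that the programme causes an SAE in 10% of participants who would not otherwise have one. With background rate c, the test-arm rate is c + 0.10(1 − c).

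| Background c | Test-arm rate | Power | Smallest excess with 80% power |
|---|---|---|---|
| 5% | 14.5% | 49% | 15.3 points |
| 10% | 19% | 34% | 18.1 points |
| 20% | 28% | 20% | 21.2 points |
| 30% | 37% | 14% | 22.7 points |
| 50% | 55% | 9% | 22.5 points |

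Part of the fall in power arises because the observable excess shrinks, from 9.5 points to 5, as more participants already have an SAE. With 51 per arm the powers are 36%, 25%, 15%, 11% and 7%.

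**5. Grades 1–2.** No arithmetic applies. The harms named in 2.2 and 6.4 reach the 9.4 comparison only if they are graded 3 or higher, and no schedule, recording rule or table covers them below that.

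**The case against.** The plan has more safeguards than a quick reading suggests.

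- Section 9.4 already classifies SAEs by causality, and the committee's power to stop is tied to danger caused by the intervention, so it does not rest on the raw rate alone. Quality-of-life decline is a further indirect check.
- Nothing restricts reporting to the test arm. Controls can report in the app, and the 8.3 interviews are not limited to one arm. The asymmetry is inferred from the absence of a control coach.
- Claims data are collected in both arms and checked with the survivor every 30 days, and health records are requested from all participants. Admissions could be found without a coach.
- Participants complete an exertion form after each session.

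Much of this stands, and it rules out several stronger readings. A reader might infer that every medical consultation counts as an SAE; the Grade 3 entry opens with the word Severe, so that is only one reading of an ambiguous line. A reader might treat 8.4 as a toxicity rule for the escalating exercise; it is an SAE definition, and 6.3 says that no dose-modification criteria are predefined. A reader might add up the healthcare contacts in 9.7, such as "Unplanned Hospitalisations" (5 against 4), to get an SAE count. Those rows give no unit or period and are planning targets for exploratory outcomes; one episode could appear in several rows, and fewer admissions would be a genuine safety benefit. Finally, a reader might conclude that the comparison is incapable of showing harm. That goes too far, since deaths and admissions depend less on who reports them.

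The safeguards do not close the gap, however. The interviews have no stated frequency. The exertion form belongs to coached sessions and serves feedback. Neither 8.4 nor 9.4 feeds records or claims into the SAE count. The planned arm comparison is of all SAEs, whatever their cause.

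**Conclusion.** The concern holds in a limited form: the SAE comparison in 9.4 is weak and open to ascertainment bias, and the expected low-grade harms have no defined place in the analysis. The missing capture of Grade 1–2 events follows directly from 6.1, 8.4 and 9.4. Unequal reporting is an inference, but a firm one, because no control-arm coach exists to use that route. Dilution depends on how the Grade 3 and Grade 4 wording is applied.

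The size of either bias cannot be fixed from the documents. Across the assumed reporting shares, the spurious risk ratio runs from 1.19 to 1.5. Across background rates of 5% to 50%, power for a 10% programme-caused excess falls from 49% to 9% at 73 per arm. These figures show that the effects could matter; they do not estimate what will happen. The change should be made, but the point does not bear on the primary FACT-G analysis.

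**What to change.** 1. Add one identical prompted safety question, covering all grades, to the scheduled app forms or to the 30-day contacts that 6.1 already gives both arms through month 18. The fortnightly columns stop at week 48, so the 30-day contacts are needed for the follow-up phase. Base the arm comparison on these prompted reports and list coach-only reports separately.
2. In 9.4, add an all-grade table by arm. Show musculoskeletal and exercise injuries (strains, joint injuries) separately from fatigue and worsening of underlying conditions, because 2.2 expects the programme to reduce fatigue and a fall there could mask injuries. Keep all-cause SAEs and show planned admissions separately. Present SAEs that the physician categorizes as related as supportive only: that judgement rests on discussion with participants, and section 8 concedes that they cannot be blinded.
3. Reconcile the Grade 3 and Grade 4 wording in 8.4 with the statement in the same section that grading is aligned with CTCAE.

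The cost is one extra app question and revised text in 6.1, 8.4 and 9.4. Participants carry slightly more burden, and there will be more minor events to tabulate.

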 - Participants will get access to Complement Theory's 12 month Live Coactive Coaching program, focusing on Exercise and Meditation and supplemented with evidence-based information on Diet, Sleep, and other lifestyle practices, adjunct to the core treatment.
 - Each week, up to five sessions of 45 minutes each will be offered, with a recommendation for participants to engage in a minimum of three sessions to ensure adequate program exposure and benefits.
 - Each session will consist of 30 Minutes of Physical Exercise and 7 minutes of meditation. Each session will be a combination session focused on Aerobic and Strength, with flexibility and balance exercises included as supplements.
 - Participants will be allocated to Low / Moderate intensity programs based on their specific medical profile, ensuring that the exercises and meditation practices are safe, effective, and aligned with their health status and cancer treatment plan.
- Active Comparator (Control) Group
 - Participants in this group will receive access to a curated collection of publicly available guidelines for lifestyle modification. These resources, presented through a digital application, will focus on exercise, meditation, diet, and sleep, but without the live coaching or program personalization.
 - This comparison aims to evaluate the impact of personalized, interactive live Coactive coaching against self-guided learning using standard guidelines.
- The overall duration for an individual participant is anticipated to be 12 months for the active phase, with a 6 month follow-up period for long-term data collection.
- **Committees:**

- Throughout the study, safety oversight will be provided by the Trial Monitoring Committee (TMC), composed of oncologists, cancer exercise specialists and biostatisticians.
- All participants enrolled in the study will be included in the safety analysis. The Trial Monitoring Committee will be responsible for reviewing relevant safety findings related to study outcomes.

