1.2 Trial Schema

1.3 Schedule of Activities

- Step 1: Enrollment and Intervention
 - Screening (including baseline assessment)

- Randomization by recruitment to test or control groups
- Informed Consent
- Access to control and test programs
- Regular Assessments up to 18 months
- Step 2: Data Analysis
 - Interim Data analysis will be 3 months, 6 months, 12 months and 18 months data.
- Step 3: Publication
 - Publication on protocol analysis and outcomes data is expected at 12 months and the end of 18 months

Section 2: INTRODUCTION

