4.1 Description of Trial Design

- **Description of Intervention Model**

- This randomized control trial features two parallel groups: an active comparator (control) group and a treatment group, aiming for a total of 146 participants diagnosed with one of the following cancers - Breast, Colorectal, Prostate Lung and Other Cancer.

- The treatment group will be given live coactive coaching and personalized digital application program focused on Exercise and Meditation, supplemented with evidence-based facts on Diet, Sleep, and other lifestyle practices
- On the other hand, the control group will be given a digital application with expert guidelines on lifestyle modification, available publicly but with no live coaching and personalization.
- In essence, this is a superiority trial aimed at establishing that CT's program is more effective in improving outcomes.

- **Description of Trial Duration**

- The overall duration for an individual participant is anticipated to be 48 weeks (minimum 3, up to 5 days per week, 45 mins each session) for the active phase, with a 6 month follow-up period for long-term data collection.
- This duration allows for a comprehensive assessment of the intervention's immediate and sustained impacts on health outcomes and healthcare costs.

- **Method of Assignment to Trial Intervention**

- Participants in each group will be recruited transparently through online advertisements while ensuring balanced representation across cancer types.
- Blinding: The participants will not be aware if they are in control or test group.
- Number of Arms: Two – one control and one treatment group.

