4.4 Start of Trial and End of Trial

- Start of Trial: Defined by the first participant's enrollment (FPI).
- End of Trial: Marked by the last scheduled follow-up of the final participant, with an anticipated end date eighteen months post final participant enrollment to allow comprehensive long-term outcome analysis.
- Early Termination: Criteria for early trial termination will include lack of efficacy, safety concerns, or regulatory guidance, detailed in Section 10.5 with responsibilities clearly outlined for both sponsor and investigator.

Section 5: TRIAL POPULATION

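### SAE collection closes on a fixed date 18 months after it opens, while the trial runs to 18 months after the last enrolment, so later enrollees lose SAE recording before their follow-up ends

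*Protocol*

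**What the plan says.** Protocol section 8.4 states the period for collecting SAE information as two calendar dates. It starts on 15 April 2024 and closes with "End: Oct 15, 2025". No per-participant window is given.

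Section 4.4 starts the trial at the first participant's enrolment, without a calendar date, and ends it at the final participant's last follow-up, "with an anticipated end date eighteen months post final participant enrollment to allow comprehensive long-term outcome analysis". In the synopsis (1.1), the duration for one participant "is anticipated to be 12 months for the active phase, with a 6 month follow-up period for long-term data collection". Section 1.3 lists "Regular Assessments up to 18 months". Section 4.1 gives a slightly shorter version: the duration "for an individual participant is anticipated to be 48 weeks" of active phase, again followed by 6 months.

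Other text points to recording for the whole trial. Section 8.4 itself says that "all SAEs encountered during this trial will be meticulously recorded". Section 8.3 says "The Trial Monitoring Committee will oversee safety assessments and procedures throughout the trial". Section 9.4 commits to continuous monitoring of SAEs and to comparing their incidence rates between arms. Section 11.1 mentions a last planned safety assessment. None of these sets an SAE window for a participant.

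The combined protocol and SAP has the same two dates in its 8.4 and the same end-of-trial rule in its 4.4.

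**The concern.** The collection window is exactly as long as one participant's follow-up, so it leaves no room for staggered enrolment. The protocol expects staggering: 4.4 separates the first participant from the final one, recruitment is by online advertisement (5.1, 6.6), screen failures may be rescreened once a temporary condition resolves (5.6), and 9.5 names slow recruitment as a ground for futility.

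If staff follow 8.4 literally, SAE recording stops while later enrollees are still on study. The loss falls first on the 6 months after coaching that the synopsis reserves for long-term data. The Trial Monitoring Committee's six-monthly decision on continuing (10.2) and the between-arm comparison in 9.4 would then rest on incomplete follow-up. A rate computed over full follow-up time would also be too low, because part of its denominator was not under SAE observation.

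Neither schedule in 6.1 has an SAE row, and the safety interviews in 8.3 have no stated timing, so no other scheduled procedure closes the gap.

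**Working it through.** **Inputs.** SAE window 15 April 2024 to 15 October 2025 (8.4). Trial end = last enrolment + 18 months (4.4). Follow-up 12 + 6 months (1.1) or 48 weeks + 6 months (4.1). Planned enrolment 146 (9.7). The accrual period is not given, so 3, 6 and 12 months are assumptions, with uniform accrual from 15 April 2024.

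**Window length.** 15 April 2024 + 18 calendar months = 15 October 2025, which is 548 days.

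**Latest enrolment still fully covered.**
- 12 + 6 months: 15 April 2024 only. A participant enrolled *a* months later loses the last *a* months.
- 48 weeks + 6 months: 336 + 183 = 519 days; 548 − 519 = 29 days of slack, so 14 May 2024.
- 24 weeks + 12 months (combined document): 30 April 2024.

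**Date to which collection would have to run under 4.4.** Accrual of 3, 6 or 12 months requires 15 January 2026, 15 April 2026 or 15 October 2026. That is 92, 182 or 365 days after the stated close.

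**Planned time lost, 12 + 6 months.** Planned time is 146 × 18 = 2,628 participant-months. With accrual over A months the mean loss is A/2 per participant:
- A = 3: 146 × 1.5 = 219; 219/2,628 = 8%
- A = 6: 146 × 3 = 438; 438/2,628 = 17%
- A = 12: 146 × 6 = 876; 876/2,628 = 33%

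Post-coaching loss is the mean of min(a, 6), that is 1.5, 3 and 4.5 of 6 months. Coaching loss is the mean of max(a − 6, 0), that is 0, 0 and 1.5 of 12 months. Check at A = 12: 4.5 + 1.5 = 6 of 18 months, or 33%.

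**Planned time lost, 48 weeks + 6 months.** With A in days, the mean loss is (A − 29)²/(2A):
- A = 91.3: 62.3²/182.6 = 21.3 days; 21.3/519 = 4%
- A = 182.6: 153.6²/365.2 = 64.6 days; 64.6/519 = 12%
- A = 365.25: 336.25²/730.5 = 154.8 days; 154.8/519 = 30%

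At A = 365.25, coaching loss is 153.25²/730.5 = 32.2 days of 336, which leaves 154.8 − 32.2 = 122.6 days lost of the 183 after coaching. At the shorter accruals all of the loss is after coaching.

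| Assumed accrual | All time, 12 + 6 m | Post-coaching | Coaching | All time, 48 wk + 6 m | Post-coaching | Coaching |
|---|---|---|---|---|---|---|
| 3 months | 8% | 25% | 0% | 4% | 12% | 0% |
| 6 months | 17% | 50% | 0% | 12% | 35% | 0% |
| 12 months | 33% | 75% | 12.5% | 30% | 67% | 10% |

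**Participants cut off while still in coaching.** These are participants enrolled after 15 October 2024 (day 183, 12-month phase) or after 13 November 2024 (548 − 336 = day 212, 48-week phase). At 12 months' accrual: 182.25/365.25 = 50% (73 of 146) or 153.25/365.25 = 42% (61 of 146). At 3 or 6 months' accrual: none.

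**The case against.** The strongest reply is that the dates may be only the planned trial dates. The window equals the 18-month trial length, and the promise to record all SAEs, the continuous monitoring in 9.4 and the oversight in 8.3 all suggest that recording would continue. The 24-hour IRB duty in 8.4, the late-reporting deviation in 9.9 and the late-reporting limit in 11.1 run from awareness of an event, with no calendar cut-off. If staff did keep recording, the actual loss could be nil. This limits the consequence but does not remove the conflict: the dates stand under the heading for the collection period, nothing labels them as planned, and they contradict the recording promise in the same section.

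Second, claims data, claim validation and progression status continue every 30 days in months 7 to 18 in both arms (6.1), and 8.4 counts hospitalization as an SAE. Many serious events would therefore leave a trace after the closing date. That is true, but claims and health records are not SAE reports and carry no grading or causality assessment.

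Third, the size is assumed. The 48-week reading gives smaller figures, which are shown above. The percentages are of planned time: with the roughly 30% drop-off expected in 9.7, part of that time would not have been observed anyway. Both points stand. The 18-month reading nevertheless has the better support (1.1, 1.3, 4.4).

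Fourth, 1.3 lists randomization before informed consent, so a window opening at consent might seem to start late. Section 6.1 places consent at baseline, 9.9 treats study activity before consent as a major deviation, and 10.1 requires consent before participation. Consent first is the supported order.

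**Conclusion.** The concern holds. As written, 8.4 and 4.4 cannot both be met unless essentially everyone enrols at the start, and the combined document repeats the conflict.

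The size cannot be fixed from the documents. It ranges from about 4% to 33% of planned participant-time across the two readings of follow-up and assumed uniform accrual of 3 to 12 months. Loss during coaching appears only at the 12-month assumption. If anyone enrolled before 15 April 2024, the fixed start date would instead miss their early SAEs.

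The two arms share the window and are randomized concurrently, so the loss is about equal between them. It costs completeness and does not by itself bias the comparison, and the FACT-G primary endpoint is untouched. It should be fixed.

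A smaller related point: 8.4 lets coaches report SAEs for participants, and only the test arm has coaches. The effect of that cannot be quantified from the documents.

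**What to change.** In 8.4, replace the two calendar dates with a per-participant window, from informed consent to the month-18 assessment or trial exit, and align it with 4.4. If the dates are only planned trial dates, label them so and state the collection window separately. Make the same change in the combined document if it remains in force.

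In 9.4, compare SAEs occurring after randomization, per person-time observed, with reports from every source kept. List SAEs before randomization separately, since baseline spans Day -30 to -1.

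As an optional addition, put one identical SAE question on the 30-day in-app forms for both arms and record the source of each report. The main correction does not depend on this.

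The cost is wording in two sections, plus one form item and one source field if the addition is taken up. SAE recording, with its 24-hour IRB reporting, runs longer by the length of accrual (3 to 12 months under the assumptions above), which the promise to record all SAEs during the trial already implies. The optional question adds up to 6 + 12 = 18 items per participant.
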